The doses will be escalated until participants are on their full dose by 1 month. If a patient encounters intolerable side effects at full dose, then they will be able to remain on the highest dose regime that they can tolerate and this dose will be recorded. The total duration of the trial drug administration will be 1 year.

Note that no maximum time since the index lacunar ischaemic stroke will be set – patients will be eligible for the trial for several years after their lacunar stroke at the discretion of the local medical staff, as long as the index stroke was compatible with lacunar ischaemic stroke and competing pathologies as a cause of the stroke were excluded using contemporaneous MR imaging, or CT, as above. That is, that the index stroke was not a non-lacunar stroke, that it was ischaemic and not haemorrhagic, and that it was not a non-stroke based on clinical and MR imaging, or CT, acquired at the time of the stroke.

Note also that no minimum cut off cognitive score is set. The Montreal Cognitive Assessment (MOCA) will be collected at baseline but will not be an inclusion/exclusion criterion. The important point is that the patient has capacity to consent, in the opinion of the randomising doctor.

[figure not shown]
Throughout the trial, patients will continue to take their normal prescribed medication which will include stroke secondary prevention prescribed since their event as per national guidelines/usual post-stroke care in participating centres.

Four hundred patients will be recruited from UK stroke research network centres. The most active of these sites see 10-15 patients per month with suspected lacunar stroke, of whom 25-33% would be eligible. Some interested sites have indicated that they could randomise 1-2 per month. Patients will be recruited from hospital-based stroke services, including patients who have participated in previous completed studies and indicated that they would like to be informed of future stroke studies.

On entry to the study, participants will be assessed by the study researcher, including presenting history, past medical history, medication history, neurological examination, check of brain MR or CT scan, blood pressure measurement and cognitive testing. They will then be randomised.

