5.5 RANDOMISATION

5.5.1 Randomisation Procedures

The electronic randomisation system and trial database are hosted by the University of Nottingham. Randomisation involves minimisation on key prognostic factors including: age, sex, stroke severity (NIHSS), dependency resulting from the stroke, systolic blood pressure $\leq/ > 140$, smoker status, time after stroke, years of education. Years of education give an estimate of pre-morbid cognitive ability and predicts post-stroke cognitive impairment; BP and smoking predict recurrent stroke; delay since stroke reflects disease activity; age, sex and stroke severity are standard minimisation variables. This approach ensures concealment of allocation (note allocation concealment means that it is not possible to guess which treatment the next patient will be randomised to), minimises differences in key baseline prognostic variables, and improves statistical power. Randomisation will not be minimised by Centre because this may result in high rates of allocation prediction, but a pre-specified post-hoc analysis by centre will be performed to investigate and adjust for heterogeneity of treatment effect by centre.

Randomisation will allocate a trial treatment, which will be prepared by the local participating Pharmacy.

Note that randomisation will be performed during normal office hours (09.00 – 17.00) and the trial allows for randomisation to occur months or years after the stroke. Therefore, in the event of computer failure (for example: server failure), the investigator will wait until the computer system is re-established to perform the randomisation. Normally, this would only be a few minutes to two hours. However, if this delay requires the patient to return on a separate occasion to collect the drugs, then a separate appointment will be made and the patient's travel expenses covered as per other trial visits.

Patients will be randomised to one of the following at a 1:1 ratio as per Section 6.2:

- cilostazol versus no cilostazol
- isosorbide mononitrate versus no isosorbide mononitrate

resulting in a partial factorial comparison of cilostazol versus isosorbide mononitrate versus both drugs versus neither drug.

The randomisation algorithm will allocate a unique identifier which will be used to label the treatment pack containing the appropriate drug made up for the patient and dispensed by the local Pharmacy.

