Participants with an indication for or contraindication to one of the trial drugs may still be randomised to the other trial drug. If a participant allocated to both trial drugs develops a contraindication to one of the trial drugs after randomisation into the trial, then they should discontinue that drug but continue to take the other trial drug. If a patient has to discontinue either or both drugs, they should continue to be followed up in the trial as planned (unless they withdraw from the trial). Patients should remain in follow up until the end of the trial follow up period, even if they discontinue trial drug, unless they withdraw from the trial.

The study will be performed open label. Placebo tablets are not available and masking by encapsulation is too complicated and expensive. However, blinding of outcomes is important to obtain unbiased information about tolerability, safety and efficacy. As such, structured symptom questionnaires, ascertainment of clinical outcomes and MRI analysis will be collected by individuals blinded to treatment allocation.

Treatment Allocation: Participants randomised to start drug will be provided with their allocated drug/s after randomisation at the baseline visit, which they will start on the next day (i.e. day 1, week 1). In the event that there is any delay between receiving the trial tablets and starting the treatment, then the patient will receive a reminder telephone call shortly before the day that the medication should be commenced. The first day of treatment defines day 1, week 1.

Participants will be supplied with trial tablets from the hospital pharmacy to cover a maximum period of six months. Detailed dated instructions on dosing will be provided in the patient pack. The participant will be telephoned between the end of weeks 1 and 2 and between the end of weeks 3 and 4, and other times during drug introduction as necessary, as well as follow-up time points, to ensure they are taking the medication correctly.

Drugs will be provided in their packs as marketed and licensed (i.e unaltered) and dispensed by the participating hospital pharmacy under research protocols.

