Haematology (full blood count) and Biochemistry (urea, electrolytes, creatinine) – most recent value obtained since time of index stroke is acceptable unless clinical reason to expect change		X ^s				
Blood pressure		X ^s				X ^s [‡]
Cognitive test: document years of education; Montreal Cognitive Assessment (MOCA)		X ^s				
Timed Trail Making Test B		X ^s				X ^s [‡]
Dispense trial medication ²		X ^s			X ^s	
Structured questionnaire: symptoms; medication history and IMP tablet adherence			X ^s	X ^s	X ^c	X ^c
Structured questionnaire: recurrent vascular events, mRS, TICS, t-MOCA, SIS, ZUNG					X ^c	X ^c
Obtain IQCODE (post/phone) from relative						X ^c
Follow-up brain MRI						X ^s
Health Economics data: EQ-5D-5L, EQ-VAS						X ^c
Adverse event / con meds reporting as necessary			X ^s	X ^s	X ^{s,c}	X ^{s,c}

[†] Consent will be obtained before the data collection procedures commence or randomisation is performed. Randomisation occurs at the end of the baseline visit.

[‡] at 12 months in some centres only.

² Dispensing in 3-monthly intervals is allowed.

^s Assessment performed by local site team.

^c Assessment performed by blinded assessor who is part of the central trial team.

SIS: Stroke Impact Scale; TICS: telephone interview for cognitive status; t-MOCA: telephone MOCA.

SECTION 4. STATISTICAL PRINCIPLES

Confidence and p values**16 Level of statistical significance**

The results of analyses and comparisons will be shown with $p < 0.05$.

17 Multiplicity

No adjustment will be made for multiplicity.

18 Levels of confidence intervals

The results of analyses and comparisons will be shown with 95% confidence intervals.

19 Adherence

19a Definition: 75% of patients will be able to tolerate trial medication, in at least half dose, up to one year after randomisation (i.e. less than 25% will stop trial medication completely through inability to tolerate the drugs).

19b Adherence presentation: See Table 4.

19c Protocol deviations: Protocol violations will be reported to the sponsor within 24 hours of becoming aware of the violation. Protocol deviations will be recorded in a protocol deviation log with these submitted to the sponsors every 3 months.

19d Protocol deviation presentation: Listing of violations and deviations and their frequency.

20 Analysis populations

Three populations are defined:

1. Intention-to-treat: All consented participants with a primary outcome measure.

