Respiratory	xx (xx.x)	xx (xx.x)	(xx.x, xx.x), p=0.xxx	xx (xx.x)	xx (xx.x)	(xx.x, xx.x), p=0.xxx
Gastrointestinal	xx (xx.x)	xx (xx.x)	(xx.x, xx.x), p=0.xxx	xx (xx.x)	xx (xx.x)	(xx.x, xx.x), p=0.xxx
Genitourinary	xx (xx.x)	xx (xx.x)	(xx.x, xx.x), p=0.xxx	xx (xx.x)	xx (xx.x)	(xx.x, xx.x), p=0.xxx
Secondary	xx (xx.x)	xx (xx.x)	(xx.x, xx.x), p=0.xxx	xx (xx.x)	xx (xx.x)	(xx.x, xx.x), p=0.xxx
Haematological	xx (xx.x)	xx (xx.x)	(xx.x, xx.x), p=0.xxx	xx (xx.x)	xx (xx.x)	(xx.x, xx.x), p=0.xxx
Metabolic/endocrine	xx (xx.x)	xx (xx.x)	(xx.x, xx.x), p=0.xxx	xx (xx.x)	xx (xx.x)	(xx.x, xx.x), p=0.xxx
Musculoskeletal	xx (xx.x)	xx (xx.x)	(xx.x, xx.x), p=0.xxx	xx (xx.x)	xx (xx.x)	(xx.x, xx.x), p=0.xxx
Infection/sepsis	xx (xx.x)	xx (xx.x)	(xx.x, xx.x), p=0.xxx	xx (xx.x)	xx (xx.x)	(xx.x, xx.x), p=0.xxx
Tumour/malignancy	xx (xx.x)	xx (xx.x)	(xx.x, xx.x), p=0.xxx	xx (xx.x)	xx (xx.x)	(xx.x, xx.x), p=0.xxx
Other	xx (xx.x)	xx (xx.x)	(xx.x, xx.x), p=0.xxx	xx (xx.x)	xx (xx.x)	(xx.x, xx.x), p=0.xxx
Total	xx (xx.x)	xx (xx.x)	(xx.x, xx.x), p=0.xxx	xx (xx.x)	xx (xx.x)	(xx.x, xx.x), p=0.xxx

Table 8. Targeted symptoms occurring at any time on treatment on isosorbide mononitrate (ISMN), cilostazol (cil) or both.

Data are number (%); comparison by binary logistic regression.

	ISMN	No ISMN	Difference (p)	Cil	No cil	Difference (p)	ISMN /Cil	No ISMN /Cil	Difference (p)
Headache	xx (xx.x)	xx (xx.x)	(xx.x, xx.x), p=0.xxx	xx (xx.x)	xx (xx.x)	(xx.x, xx.x), p=0.xxx	xx (xx.x)	xx (xx.x)	(xx.x, xx.x), p=0.xxx
Stopped normal activities	xx (xx.x)	xx (xx.x)	(xx.x, xx.x), p=0.xxx	xx (xx.x)	xx (xx.x)	(xx.x, xx.x), p=0.xxx	xx (xx.x)	xx (xx.x)	(xx.x, xx.x), p=0.xxx
Palpitations	xx (xx.x)	xx (xx.x)	(xx.x, xx.x), p=0.xxx	xx (xx.x)	xx (xx.x)	(xx.x, xx.x), p=0.xxx	xx (xx.x)	xx (xx.x)	(xx.x, xx.x), p=0.xxx
Stopped normal activities	xx (xx.x)	xx (xx.x)	(xx.x, xx.x), p=0.xxx	xx (xx.x)	xx (xx.x)	(xx.x, xx.x), p=0.xxx	xx (xx.x)	xx (xx.x)	(xx.x, xx.x), p=0.xxx
Dizziness	xx (xx.x)	xx (xx.x)	(xx.x, xx.x), p=0.xxx	xx (xx.x)	xx (xx.x)	(xx.x, xx.x), p=0.xxx	xx (xx.x)	xx (xx.x)	(xx.x, xx.x), p=0.xxx
Stopped normal activities	xx (xx.x)	xx (xx.x)	(xx.x, xx.x), p=0.xxx	xx (xx.x)	xx (xx.x)	(xx.x, xx.x), p=0.xxx	xx (xx.x)	xx (xx.x)	(xx.x, xx.x), p=0.xxx
Loose stools	xx (xx.x)	xx (xx.x)	(xx.x, xx.x), p=0.xxx	xx (xx.x)	xx (xx.x)	(xx.x, xx.x), p=0.xxx	xx (xx.x)	xx (xx.x)	(xx.x, xx.x), p=0.xxx

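### SAP Table 8 counts targeted symptoms only while on treatment but sets no counting window for patients with no drug to stop; if only drug-allocated patients are cut at stopping, the comparison leans towards apparent safety

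*SAP*

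**What the plan says.** SAP Table 8 is headed "Targeted symptoms occurring at any time on treatment on isosorbide mononitrate (ISMN), cilostazol (cil) or both". Its columns are ISMN and no ISMN, cilostazol and no cilostazol, and both drugs and neither. The method line reads "Data are number (%); comparison by binary logistic regression"; there is no person-time, offset or censoring.

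The SAP does not say what on treatment means, gives no window for the no-drug columns and names no analysis set for this table. The safety population in SAP section 20 requires a dose of randomised drug to have been taken, which a patient allocated to neither drug cannot satisfy. By contrast, SAP Tables 4, 5, 7a-c and 9 are presented by randomised group.

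The symptom data do not stop when the drug stops. Protocol section 5.5.1 says "Patients should remain in follow up until the end of the trial follow up period, even if they discontinue trial drug". SAP Table C schedules the "Structured questionnaire: symptoms; medication history and IMP tablet adherence" at weeks 1-2 and 3-4 and at months 6 and 12, with no distinction by group.

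**The concern.** Read literally, the title gives the two sides of the comparison different windows. A drug-allocated patient who stops in the first month contributes one or two questionnaires. A never-treated patient has nothing to stop and, unless told otherwise, an analyst would count all four. The outcome is ever having the symptom, so a shorter window lowers the count whatever the drug does. The other literal reading, on treatment applied to everyone, empties the neither column.

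Protocol section 1.2 names headache, bleeding, and postural hypotension with falls among the points on which information is lacking. Protocol section 10.3.2 classes headache, dizziness, palpitations, bruising and falls as outcome events, which go no further as adverse events unless serious and possibly related. The serious adverse event tables therefore do not replace Table 8: for the non-serious forms of these symptoms it is the only comparison in the SAP.

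**Working it through.** The plan gives no figure for Table 8, so there is nothing to reproduce. The check asks what the on-treatment count would show for a drug with no effect.

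**Inputs from the documents**
- Four questionnaires (SAP Table C).
- Stopping limit: "less than 25% will stop trial medication completely through inability to tolerate the drugs" (SAP sections 19a and 26a). The timing of stopping is not given.
- 363 recruited (SAP Table 2). Allocation is 1:1 for each drug (protocol section 5.5.1). If all enter both randomisations, 363/2 ≈ 182 per side for each main comparison and 363/4 ≈ 91 per group for dual versus neither.
- Two-sided 5% level (the SAP gives p<0.05; two-sided is assumed).

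**Assumptions**
- Symptom risk per questionnaire q = 10%, 15% or 20%, equal in all groups and independent between questionnaires.
- 25% of drug-allocated patients stop after k = 2 or k = 1 questionnaires, for reasons unrelated to the symptom counted.
- Never-treated patients are counted for all four questionnaires.

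**Formulas**
- Full window: f = 1 − (1 − q)^4
- Stopper: s = 1 − (1 − q)^k
- Drug-allocated patients: r = 0.75f + 0.25s
- No ISMN, or no cilostazol, when the half allocated the other drug is also cut: c = (f + r)/2

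| q | k | f | r | c |
|---|---|---|---|---|
| 10% | 2 | 34.4% | 30.5% | 32.5% |
| 10% | 1 | 34.4% | 28.3% | 31.3% |
| 15% | 2 | 47.8% | 42.8% | 45.3% |
| 15% | 1 | 47.8% | 39.6% | 43.7% |
| 20% | 2 | 59.0% | 53.3% | 56.2% |
| 20% | 1 | 59.0% | 49.3% | 54.2% |

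**One case by hand:** dual versus neither, q = 10%, k = 1. The difference is 0.3439 − 0.2829 = 0.0610 and the mean risk is 0.3134. The standard error is √(2 × 0.3134 × 0.6866/91) = 0.0688, so the shift is 0.0610/0.0688 = 0.89 standard errors. The chance of a falsely protective result is Φ(0.89 − 1.96) ≈ 14%; the chance of a falsely harmful one is about 0.2%.

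**False rejection, simulated (unadjusted Pearson chi-square)**

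| q | k | Dual v neither, 91 per group (r v f) | Main comparison, other drug's patients also cut, 182 per group (r v c) | Main comparison, other drug's patients not cut, 182 per group (r v f) |
|---|---|---|---|---|
| 10% | 2 | 9% | 7% | 12% |
| 10% | 1 | 14% | 10% | 24% |
| 15% | 2 | 10% | 8% | 16% |
| 15% | 1 | 19% | 12% | 35% |
| 20% | 2 | 12% | 9% | 20% |
| 20% | 1 | 25% | 16% | 47% |

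Most of these rejections point towards protection. With 15% stopping after two questionnaires, the first two columns of results fall to about 5-7%. With one common window for all groups the rate returns to 5%.

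**Second model, constant hazard.** Assume a 12-month symptom risk of 20%, 30% or 50% and 25% stopping. The chance of a falsely protective result (nominal 2.5%) is:
- dual versus neither: 12-32% if all stop at one month, 6-11% if stopping is spread evenly over the year;
- main comparisons with the other drug's patients also cut: 8-19% and 5-8%.

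The direction is the same. The size depends on how early patients stop.

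**The case against.** The strongest reply is that the unequal window is not written down. Table 8 is an empty shell; no rule for cutting at the stop date appears, and nothing says that never-treated patients are counted for the whole year. Since "The total duration of the trial drug administration will be 1 year" (protocol section 3), the title could mean the one-year treatment period, common to all groups. The SAP's general statement under Minimising bias, that all participants are analysed, fits that reading. This stands as far as it goes: the bias is conditional. But the common-window reading is stated nowhere for this table, and it is what the fix would make explicit.

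A reader might also infer that false rejection reaches 12-47% in the main comparisons. The documents do not support that as the general case. The design is factorial, "resulting in a partial factorial comparison of cilostazol versus isosorbide mononitrate versus both drugs versus neither drug", so about half of no ISMN is allocated cilostazol, and the reverse. The title covers both drugs, so those patients would naturally be cut as well. The higher range needs them left uncut.

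Nor is Table 8 the main comparison for bleeding: SAP section 27a compares systemic and intracranial bleeding between groups with no on-treatment limit, and Tables 7a-c compare serious events by randomised group.

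Two further points stand. The 25% is the plan's tolerability limit, not its expected rate. And a symptom that itself caused stopping is already counted, so the cut loses nothing for that symptom in that patient. On-treatment reporting of acute side effects is also a recognised choice, but as a comparison with untreated patients it needs a stated window on both sides.

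**Conclusion.** The point holds in conditional form and should be corrected. Table 8 states a counting rule that cannot be applied to the neither group as worded and, on its most literal workable reading, gives drug-allocated patients the shorter window. The bias then runs towards no harm.

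Under no drug effect, 25% stopping after one or two questionnaires and a 10-20% risk per questionnaire, false rejection is about 9-25% for dual versus neither. It is about 7-16% for the two main comparisons with the other drug's patients also cut. It is near nominal, about 5-7%, with 15% stopping after two questionnaires. Symptom risks, stopping times and full entry into both randomisations are assumptions; covariate adjustment is ignored.

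The primary endpoint is unaffected. What is at stake is the reading of headache, dizziness, palpitations, bruising and falls, most of all in dual versus neither. The SAP calls that comparison very underpowered but keeps it because those may be the two groups in the follow-on trial.

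**What to change.** Make the main Table 8 a count of targeted symptoms at any time from randomisation to 12 months, by randomised group, using all four questionnaires whether or not the patient is still taking drug. State that the analysis set is all randomised participants, including those allocated to neither drug. If an on-treatment view is wanted, define it (for example, up to the recorded stop date) and show it as a descriptive supplement for drug-allocated patients only, with time on drug alongside.

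The cost is SAP wording: the questionnaires are already scheduled for all groups and continue after stopping. The downside is that time off drug enters the count, which slightly dilutes acute on-drug effects; the supplement keeps those visible.
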